#### 11.3.3 IBS Quality of Life Questionnaire

The responses to each of the 34 questions on the IBS-QOL will be summarized with frequencies and percentages of subjects reporting each category by IBS subtype, including combined, treatment group within

subtype, and visit. Missing values will not be reported so the denominator for percentages will be the number of subjects with a response for the visit in the subtype/treatment group.

The mean overall total score and the 8 subscale scores and mean changes from baseline will be summarized by IBS subtype (including combined), treatment group, and visit. Means for subscales with questions missing responses will not be calculated. P-values from t-tests comparing mean change from baseline between Blautix and placebo will be presented at each post-baseline visit for exploratory purposes.

All response data from the IBS-QOL and the derived scores will be listed.

#### **11.3.4 IBS Symptom Severity Score**

The IBS-SSS mean scores from Part 1 and mean changes from baseline will be summarized by IBS subtype (including combined), treatment group, and visit. P-values from t-tests comparing mean change from baseline between Blautix and placebo will be presented at each post-baseline visit for exploratory purposes.

Analyses of the IBS-SSS will be repeated excluding data that was collected over the phone and transcribed due to COVID-19 remote visits. If notable differences are observed with and without these visits, additional analyses may be completed to properly control for this change in methodology.

All response data from the IBS-SSS will be listed (ie Part 1 and Part 2).

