## 6. GENERAL ANALYSIS CONSIDERATIONS

The statistical analyses will be reported using summary tables, listings, and figures (TLFs). The International Council for Harmonisation (ICH) numbering convention will be used for all TLFs. Statistical testing of the primary efficacy endpoint will be one-sided and will be performed at the 0.10 significance level. For the primary efficacy endpoint, two-sided 80% confidence intervals (CI) will be presented and the 95% confidence interval will be presented as an exploratory analysis. Unless stated otherwise, statistical testing of other efficacy endpoints will be two-sided and will be performed at the 0.05 significance level, and 95% CIs will be presented. Differences in means produced by t-tests will be calculated using the Satterthwaite method.

Continuous variables will be summarized with means, standard deviations, medians, minimums, and maximums.

Categorical variables will be summarized by frequency and by percentage of subjects in corresponding categories. Percentages for missing values are omitted and do not account for the percent calculation of other categories. Percentages are routinely based on the total category count excluding the missing category if not otherwise mentioned. Footnotes will specify the percent basis in other cases.

Generally, summary tables will be presented by treatment group within each of the IBS subtypes (IBS-C and IBS-D). As appropriate, treatment group summaries and analyses will be done by combining the subtypes. Demographic, baseline summaries, and prior/concomitant medication summaries will additionally include summary columns with totals across the subtype groups for each subtype and overall.

Individual subject data obtained from the eCRFs, external vendors, the eCOA system, central clinical laboratory, electrocardiogram (ECG), and any derived data will be presented by IBS subtype, treatment, and subject in data listings.

The analyses described in this plan are considered a priori, in that they have been defined prior to database lock and breaking the study blind.

Any analyses performed subsequent to breaking the blind will be considered post hoc and exploratory. Post hoc analyses will be labeled as such on the output and identified in the CSR.

All analyses and tabulations will be performed using SAS® software Version 9.4 or higher. Tables, listings, and figures will be presented in RTF format.

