## 11.2 Additional Analyses of the Primary Efficacy Endpoint

As a sensitivity analysis, the primary efficacy analysis of the overall response rate will be repeated for the Efficacy Evaluable Set.

The remaining additional summaries and analyses will be done using the FAS.

The overall response rate will be analyzed with the IBS subtypes combined. A CMH test stratified by subtype will be used to test for an overall difference between the treatment groups across the subtype strata. To correspond with the primary analysis, the significance level will be two-sided 0.20 and an 80% CI for the treatment difference will be provided.

The primary efficacy endpoint (overall response) will be summarized and analyzed using the same method as the primary analysis by subgroups formed by sex and by region (US, UK and Ireland). The CMH analysis of overall response stratified by subtype will also be presented by sex and by region.

The frequencies and percentages of responders and non-responders by week during the treatment period will be summarized by IBS subtype and treatment group. A summary for the subtypes combined will be included. No CIs or inferences will be given.

The overall response rate will be further analyzed using a logistic regression model for each subtype. The models will include treatment and region (US, UK and Ireland) as factors and the baseline week average of Abdominal Pain Intensity and the subtype-specific baseline value as covariates. For the IBS-D model, the baseline covariate will be the proportion (as %) of days during the consecutive week prior to baseline, used for assessment of eligibility assessment, with at least one bowel movement Type 6 or 7. For the IBS-C model, the baseline covariate will be the average stool frequency in the week prior to baseline as noted for IBS-D. Model based odds ratios will be reported with 95% CIs.

The weekly average Abdominal Pain Intensities, the Abdominal Pain Intensity differences (baseline – weekly average, such that positive differences indicate improvement), and the percent differences [ $100 * (\text{baseline} - \text{weekly average}) / \text{baseline}$ ] will be summarized by IBS subtype (including combined), treatment group, and week across the treatment period and follow-up.

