The weekly average Abdominal Pain Intensity differences during the treatment period (not including follow-up) will be further analyzed using linear models for repeated measures. The models will include treatment, region, and week as main effects, treatment-by-week as an interaction term, and the baseline week Abdominal Pain Intensity as a covariate. Separate models will be built for each IBS subtype and for the subtypes combined. The IBS subtype will be included in the model for combined subtypes as a fixed effect. The covariance matrix will be unstructured. If there are convergence issues, corrected AIC will be used to

choose between the following covariance structures: Toeplitz, heterogeneous autoregressive (1) [ARH(1)] and autoregressive(1) [AR(1)]. The method of Kenward and Roger will be used to estimate denominator degrees of freedom.

Least squares (LS) means and their standard errors (SE) from the MMRM models for the weekly average Abdominal Pain Intensity differences by IBS subtype, treatment group, and week with 95% CIs will be presented. The LSM and SE of the treatment differences from placebo will also be presented with 95% CIs and p-values from t-tests for a difference from 0.

Listings of daily assessments from the eCOA data will not be provided. However, the derived weekly endpoints and response rates will be listed by IBS subtype and treatment group.

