#### **11.3.5 Hospital Anxiety and Depression Scale**

The mean Anxiety and Depression scores for the HADS and mean changes from baseline will be summarized by IBS subtype (including combined), treatment group, and visit. P-values from t-tests comparing mean change from baseline between Blautix and placebo will be presented at each post-baseline visit for exploratory purposes. Means for subscales with questions missing responses will not be calculated.

All response data from the HADS and the derived Anxiety and Depression scores will be listed.

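### If combined-subtype p-values are produced for IBS-QOL, IBS-SSS and HADS, the unadjusted t-test leaves out IBS subtype, unlike the SAP's other combined analyses; the cost is small and the remedy nearly free

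*SAP*

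**What the plan says.** **The three questionnaires.** For IBS-SSS, SAP 11.3.4 says: "The IBS-SSS mean scores from Part 1 and mean changes from baseline will be summarized by IBS subtype (including combined), treatment group, and visit". The next sentence is: "P-values from t-tests comparing mean change from baseline between Blautix and placebo will be presented at each post-baseline visit for exploratory purposes". SAP 11.3.3 (IBS-QOL) and 11.3.5 (HADS) follow the same pattern. No stratum or covariate is named.

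**The form of the test.** SAP section 6 adds: "Differences in means produced by t-tests will be calculated using the Satterthwaite method". On pooling, the same section says: "As appropriate, treatment group summaries and analyses will be done by combining the subtypes".

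**The design.** Protocol 5.3.1 plans 250 subjects in each cohort, 125 per arm, so subtype is part of the randomisation structure.

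**The SAP's other combined inferential analyses.** For overall response, SAP 11.2 says: "A CMH test stratified by subtype will be used to test for an overall difference between the treatment groups across the subtype strata". SAP 10.6 repeats that stratified test by sex and by region. For the combined repeated-measures model of abdominal pain, SAP 11.2 says: "The IBS subtype will be included in the model for combined subtypes as a fixed effect". SAP section 13, which lists changes from the protocol analyses, does not mention the different treatment of the questionnaires.

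**The concern.** When subjects are randomised within cohorts and the cohorts are then pooled, the comparison should carry the cohort. Otherwise any difference in mean change between IBS-C and IBS-D goes into the error term. The t-test's standard error is then larger than the true sampling variability of the treatment difference, and the test is conservative.

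There is a second route. SAP 10.4 analyses observed cases, and SAP 11.3.4 repeats the IBS-SSS analyses without data collected by telephone. Neither subset is guaranteed to keep the same subtype mix in both arms at every visit. Where the mixes differ, an unstratified difference contains some of the subtype difference.

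The stake is limited to the precision and interpretation of exploratory combined comparisons.

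**Working it through.** **1. The plan's own figure.** The only design figure is the power of the primary test in Protocol 10.2: 125 per arm, 40% against 55%, one-sided alpha 10%, Yates correction, at least 80%. Exact binomial enumeration gives 82.5%, so it reproduces. It has no bearing on this point, because neither document gives an SD, effect size or power for the three questionnaires.

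**2. Effect of omitting subtype.** Let D be the difference in mean change between subtypes in within-subtype SD units, and w the share of one cohort. With 1:1 allocation in each cohort, the variance used by the unstratified test is multiplied by 1 + w(1 − w)D². With equal cohorts this is 1 + D²/4. The documents do not give D, so a range is assumed.

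To express the loss, take 250 per arm, two-sided alpha 0.05 (SAP section 6), and the effect at which the subtype-adjusted test has 80% power: (1.960 + 0.842) × √(2/250) = 0.251 SD. Under exact balance the estimate itself is no more variable; only its estimated SE is inflated, by r = √(1 + D²/4). So the type I error is 2 × [1 − Φ(1.960r)] and the power is Φ(2.802 − 1.960r).

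| D (assumed) | Variance factor | SE increase | Type I error | Power |
|---|---|---|---|---|
| 0 | 1.000 | 0% | 0.050 | 80.0% |
| 0.2 | 1.010 | 0.5% | 0.049 | 79.7% |
| 0.3 | 1.023 | 1.1% | 0.047 | 79.4% |
| 0.5 | 1.063 | 3.1% | 0.043 | 78.3% |
| 1.0 | 1.250 | 11.8% | 0.028 | 72.9% |

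A simulation of 20,000 trials per setting agrees. The unstratified test rejected a true null in 0.048, 0.050, 0.045 and 0.028 of trials at D = 0, 0.2, 0.5 and 1.0; with subtype in the model the rate was 0.048 to 0.052. In interval width, D = 0.2 costs 500 × (1 − 1/1.010) ≈ 5 of 500 subjects, and D = 0.5 costs 500 × (1 − 1/1.0625) ≈ 29. Unequal cohorts make the inflation slightly smaller: at D = 0.5 and a 30:70 split it is 0.3 × 0.7 × 0.25 = 5.3%, against 6.3% at 50:50.

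**3. Unequal subtype mixes.** If the share of one subtype differs between arms by g at a visit, the unstratified difference is shifted by g × D. Each percentage point of imbalance therefore moves it by 0.002 SD at D = 0.2 and 0.005 SD at D = 0.5. The documents give no basis for a value of g.

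**4. Adding the baseline score (a separate gain).** With baseline to follow-up correlation ρ and k = baseline SD / follow-up SD, the residual variance of the baseline-adjusted model relative to the change score is (1 − ρ²)/(1 + k² − 2ρk). Both ρ and k are assumptions.

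| ρ | k = 1 | k = 0.7 |
|---|---|---|
| 0.3 | 0.91/1.40 = 0.65 (35% lower) | 0.91/1.07 = 0.85 (15% lower) |
| 0.5 | 0.75/1.00 = 0.75 (25% lower) | 0.75/0.79 = 0.95 (5% lower) |
| 0.6 | 0.64/0.80 = 0.80 (20% lower) | 0.64/0.65 = 0.98 (2% lower) |

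A value of k below 1 is plausible for IBS-SSS, because Protocol 5.1 requires at least 175 at screening and 157.5 at baseline, which truncates the baseline distribution.

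**The case against.** **Combined p-values are not stated outright.** In SAP 11.3.3 to 11.3.5 the combined column belongs to the sentence on summaries, and the t-test sentence names no population. Protocol 10.5.2 compares secondary endpoints within each cohort, and Protocol 10.5 allows pooling only as an exploratory option. The table shells that would settle the matter are in a separate document (SAP 15.3). This stands, and it makes the point conditional. The combined reading is still the natural one, because the two sentences are adjacent and section 6 provides for combined analyses.

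**The MMRM sentence may govern.** SAP 10.4 assigns continuous assessments over time to MMRM, and the one combined MMRM that the SAP specifies includes subtype. If that rule applied to these scores, the point would fall away. The three sections, however, specify t-tests explicitly.

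**The loss is negligible and the p-values exploratory.** This largely stands. Under the assumed 0.2 to 0.5 SD gap, power falls by less than two percentage points, and these p-values drive no stated decision. The imbalance route is a possibility with no figure behind it.

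**A linear model gives up the unequal-variance protection of the Satterthwaite test.** This is true of ordinary least squares, and it is why the remedy below specifies the variance. The combined rows would also use a different method from the per-subtype rows in the same table, which is a real but small cost.

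**Conclusion.** The point holds as a minor inconsistency with a cheap remedy. On the natural reading, the combined t-tests for the three questionnaires omit the randomisation cohort, while the SAP's CMH analyses and combined pain model include it. With balanced arms the consequence is a standard error about 0.5% to 3% too large for an assumed subtype gap of 0.2 to 0.5 SD. It approaches 12% only at an assumed gap of a full SD.

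Three stronger conclusions that a reader might draw are not supported:

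- **Bias or inflated type I error.** With 1:1 allocation within cohort and complete data the difference is unbiased, and the test errs on the conservative side. Bias needs unequal subtype mixes, which is possible but unquantified.
- **A 20% to 35% loss from ignoring subtype.** That range is the gain from the baseline covariate. It would apply equally to the per-subtype t-tests, and it assumes equal baseline and follow-up SDs; with an SD ratio of 0.7 it becomes about 2% to 15%.
- **Pooling of two different diseases.** The protocol treats IBS-C and IBS-D as subtypes of one disorder, and Protocol 2.2 reports frequent movement between subgroups.

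The per-subtype t-tests and the primary per-cohort analysis are unaffected.

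**What to change.** In SAP 11.3.3, 11.3.4 and 11.3.5, first state whether p-values are produced for the combined subtypes. Wherever they are, including the repeat IBS-SSS analysis without telephone-collected data, replace the t-test by a linear model of change from baseline on treatment, IBS subtype and baseline score at each post-baseline visit. Use heteroscedasticity-robust or group-specific variances, and report the adjusted treatment difference with its 95% CI beside the p-value. The per-subtype t-tests can stay.

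The cost is a few lines of SAP text and a change of procedure in tables already planned. No new data are needed and no subject is lost: subtype comes from the IVRS and cannot be missing (SAP 8.1), and a subject without a baseline score has no change score to analyse anyway. The price is a second method in the same tables, which a footnote can explain. The change should be made before unblinding, because SAP section 6 classes later analyses as post hoc.

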5.3 Treatment assignment procedures

5.3.1 Randomisation

This is a double-blind study and subjects will randomly receive either Blautix[™] or placebo in a 1:1 ratio respectively. At Baseline (Visit 1), subjects will be classified into either the IBS- C (Cohort C) or the IBS-D (Cohort D) cohort of subjects and 250 subjects will be enrolled into each cohort. Within each cohort, 125 subjects will randomly receive Blautix[™] and 125 subjects will randomly receive matching placebo. Allocation of randomisation numbers will be performed centrally using an interactive voice/web response allocation system (IV/WRS).

Subjects, 4D pharma Plc, designated CRO and clinical site staff will be blinded to the investigational product allocation for each subject. Randomisation data will be kept strictly confidential, filed securely by the Sponsor (or designee) and accessible only to authorised persons of the Sponsor (or designee), and accessible only to authorised per Sponsor (or designee)'s standard operating procedures (SOPs) until the time of unbinding.

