10.2 Sample Size Calculation

Within each Cohort, 125 subjects per treatment group provide at least 80% power to demonstrate a statistically significant difference between the treatment groups at a one-sided alpha of 10% using Pearson's test with Yates's correction when the true response rate in Placebo group is 40% and the true response rate in the BlautixTM group is 55%.

The total planned study size is therefore 500 subjects.

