### 10.2 Baseline Values for Efficacy Assessments

For the daily assessments collected on the eCOA device, baseline values will be derived from the 7 consecutive days assessed preceding the Baseline (Day 1) visit used to assess eligibility. The baseline value will be considered missing if less than 4 of the 7 days have an assessment.

- Abdominal Pain Intensity (1-10)

- Stool Consistency (day with at least one bowel movement Type 6 or 7)
- Stool Frequency

The baseline value for each of these assessments will be calculated by summing the daily result over the 7-day period and dividing by the number of days with an assessment. The Stool Consistency baseline proportions will be multiplied by 100 to convert to a percentage.

Baseline for the other efficacy assessments is defined as the last non-missing value recorded on or before the Baseline (Day 1) visit.

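### IBS-QOL, IBS-SSS and HADS are compared by t-tests of change that leave out the recorded baseline score, giving up precision that a baseline covariate would recover at almost no cost

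*SAP*

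**What the plan says.** SAP 11.3.3 (IBS-QOL), 11.3.4 (IBS-SSS) and 11.3.5 (HADS) give descriptive summaries of scores and changes and then the same sentence: "P-values from t-tests comparing mean change from baseline between Blautix and placebo will be presented at each post-baseline visit for exploratory purposes". SAP section 6 fixes the form of the test: "Differences in means produced by t-tests will be calculated using the Satterthwaite method". It also sets the level: "statistical testing of other efficacy endpoints will be two-sided and will be performed at the 0.05 significance level". None of the three sections names a covariate, and SAP 10.3 provides covariate adjustment only for the responder endpoint.

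The baseline scores exist. The schedules in both documents have all three questionnaires completed at the Baseline visit, and SAP 10.2 defines the value to use: "Baseline for the other efficacy assessments is defined as the last non-missing value recorded on or before the Baseline (Day 1) visit".

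Two other parts of the SAP point towards a baseline-adjusted or repeated-measures analysis. The weekly abdominal pain model in SAP 11.2 includes treatment, region, week, their treatment interaction "and the baseline week Abdominal Pain Intensity as a covariate". SAP 10.4 states, in general terms, that MMRM is the method for continuous outcomes measured repeatedly. It specifies no such model for these three scores.

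Protocol 10.5.2 leaves the choice of secondary tests open to standard methods as appropriate.

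**The concern.** A t-test on change subtracts the whole baseline score, which fixes the slope of follow-up on baseline at 1. When the true slope differs from 1, as it does with similar spread at both times and a correlation below 1, the change score carries baseline noise that an estimated slope would remove.

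These are three of the five named secondary efficacy endpoints. Global relief gets no inference (SAP 11.3.1), and the number of complete spontaneous bowel movements gets a Mann-Whitney test (SAP 11.3.2). So the unadjusted t-test is the specified comparison for quality of life, symptom severity, anxiety and depression. At stake are wider intervals and lower power than the same data could give, in a Phase 2 trial whose results are meant to feed pivotal planning (Protocol 10.3). The SAP gives no reason for treating these scores differently from pain.

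**Working it through.** **Inputs from the documents.** The sample size is 125 per arm in each cohort ("Within each Cohort, 125 subjects per treatment group provide at least 80% power to demonstrate a statistically significant difference", Protocol 10.2), with allocation to Blautix or "placebo in a 1:1 ratio respectively" (Protocol 5.3.1). The secondary tests are two-sided at 0.05 (SAP section 6).

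**Inputs not in the documents.** No SD, effect size or baseline-to-follow-up correlation is given for the three scales. Assumed: correlation ρ from 0.3 to 0.7, and ratio k = baseline SD / follow-up SD from 0.6 to 1.2.

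**Step 1: the plan's own figure.** The stated power of at least 80% is for the responder comparison, 40% against 55%, "at a one-sided alpha of 10"%, using Pearson's test with Yates's correction. Exact binomial enumeration at 125 per arm gives 82.5%. The continuity-corrected formula needs 112 per arm for 80%. The figure is reproduced. The plan states no power for IBS-QOL, IBS-SSS or HADS.

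**Step 2: variance ratio.** With follow-up SD s:

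- variance of the change score = s²(1 + k² − 2ρk)
- residual variance after adjusting for baseline = s²(1 − ρ²)
- ratio R = (1 − ρ²) / (1 + k² − 2ρk)

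The denominator minus the numerator is k² − 2ρk + ρ² = (k − ρ)². So R is never above 1, and it equals 1 only when k = ρ, that is, when the slope ρ/k is 1. With k = 1, R = (1 + ρ)/2.

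**Step 3: equal SDs (k = 1).** The effect is set so that the change-score t-test has 80% power at 125 per arm, two-sided 0.05.

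| ρ | R | Variance cut | t-test SE larger by (1/√R − 1) | Power with ANCOVA | n per arm for the t-test to match (125/R) |
|---|---|---|---|---|---|
| 0.3 | 0.65 | 35% | 24% | 93.5% | 193 |
| 0.5 | 0.75 | 25% | 15% | 89.9% | 167 |
| 0.7 | 0.85 | 15% | 8% | 86.0% | 148 |

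A simulation of 4,000 trials at ρ = 0.5 and a difference of 0.354 follow-up SD gave 78.8% for the Satterthwaite t-test and 89.0% for ANCOVA, in line with the table.

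**Step 4: unequal SDs.** ANCOVA power, again from 80% for the t-test, with R in brackets:

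| k | ρ = 0.3 | ρ = 0.5 | ρ = 0.7 |
|---|---|---|---|
| 0.6 | 83.6% (0.910) | 80.5% (0.987) | 80.8% (0.981) |
| 0.7 | 85.9% (0.850) | 82.0% (0.949) | 80.0% (1.000) |
| 0.8 | 88.6% (0.784) | 84.3% (0.893) | 80.8% (0.981) |
| 1.2 | 97.1% (0.529) | 95.0% (0.605) | 92.8% (0.671) |

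For example, k = 0.7 and ρ = 0.5 gives 0.75 / (1 + 0.49 − 0.70) = 0.75 / 0.79 = 0.949.

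**Step 5: dependence on starting power.** With equal SDs and ρ = 0.5, the gain is 9.9 points from 80%, but only 1.7 points from 10% and 3.6 points from 95%.

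**The case against.** **The p-values are labelled exploratory.** This stands and limits the stakes. No power is claimed for these scales, neither document adjusts for multiplicity, and no decision is tied to the results. The label is not a reason to prefer the less precise of two equally simple analyses.

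**The t-test is a valid method.** This also stands. A reader might infer that an unadjusted change score biases these comparisons or inflates their type I error. It does neither. Randomisation makes the estimate unbiased, and the effect of chance baseline imbalance is already in its standard error. The issue is efficiency.

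**SAP 10.4 may already promise MMRM for these scores.** Read literally, it could cover them, so the t-test is not a fully settled choice. But it names no model or baseline covariate for them, and 11.3.3 to 11.3.5 specify none. It leaves an inconsistency to resolve rather than supplying the adjustment.

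**The gain may be small.** A reader might take the equal-SD figures as what all three scales would gain, or suppose that the gain is negligible only when both the correlation and the power are already high. The documents support neither. A baseline SD below the follow-up SD is plausible for IBS-SSS, because the entry floors (175 at screening, 157.5 at Baseline; Protocol 5.1) restrict baseline but not follow-up. Steps 4 and 5 show small gains at lower k, and at low or high starting power even with a moderate correlation. What the objection cannot show is a loss beyond one degree of freedom.

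**Conclusion.** The point holds as a matter of avoidable imprecision in three exploratory secondary comparisons. The planned tests are valid, and neither the primary analysis nor its stated power is affected.

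The size cannot be fixed from the documents. Starting from 80% power at 125 per arm, adjustment gives 86.0% to 93.5% if the SDs are equal and ρ lies between 0.3 and 0.7. If the baseline SD is 0.7 of the follow-up SD, it gives 80.0% to 85.9%. The gain is zero where the slope of follow-up on baseline is 1. These figures assume a linear relation and complete data at the visit. Missing scores would lower the power of both analyses but leave the variance ratio unchanged.

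Because the direction does not depend on the assumptions and the cost is trivial, the change is worth making even though the benefit is uncertain.

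**What to change.** In SAP 11.3.3, 11.3.4 and 11.3.5, within each IBS subtype, replace the t-test by one of these:

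- ANCOVA of change at each post-baseline visit, with treatment and that score's own baseline (as defined in SAP 10.2) in the model; or
- an MMRM of the form used for pain in SAP 11.2, with that score's baseline as covariate. The pain model leaves out follow-up, so the text should say whether the follow-up visit is included here.

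Report the adjusted treatment difference with its 95% CI and p-value; SAP section 6 already calls for 95% intervals. Keep the raw means and mean changes as descriptive summaries, and keep the exploratory label. Use the same model for the IBS-SSS repeat in 11.3.4 that leaves out scores taken by telephone. Reword SAP 10.4 so that it and these sections name the same method.

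The cost is SAP wording and a small programming change, with no new data or subjects. Statistically it costs one degree of freedom per model and an assumed linear baseline term. The change should be made before database lock and unblinding, since SAP section 6 would otherwise class it as post hoc. The efficacy tables that SAP 10.5 lists for the interim analysis do not include these three scores.
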